2. Modified based on the insulin titration algorithms in the BEGIN basal-bolus type 2 study [Garber, 2012] and other published treat-to-target studies [Rosenstock, 2008; Abrahamson, 2012; Mathieu, 2014; Riddle, 2014].
3. Investigator may defer adjustment if there is an obvious reason for the low value such as a missed meal.

Any insulin titration that differs from the algorithm recommended dose must be commented on by the investigator and the reason documented on the appropriate page of the eCRF. If adequate documentation is not provided in the eCRF, a protocol deviation will be recorded.

If the before breakfast glucose target has been achieved, but it is felt that the basal insulin needs further optimization, then alternatives (e.g., moving the basal injection to the morning or splitting the basal dose into twice daily injections) can be discussed with the medical monitor overseeing the titration and documented.

Insulin Lispro Titration

Insulin titration should start with insulin glargine given before bedtime. After about 6 weeks, it is expected that the basal insulin glargine dose will have been stabilized and the insulin lispro titration may begin.

Following randomization to study medication, insulin lispro will be titrated differently in each treatment group.

In the albiglutide plus insulin glargine group, the insulin lispro dose will be downtitrated at the Baseline/Randomization visit to half that used at the end of the Standardization Period. At Week 4, insulin lispro will be completely discontinued and should remain discontinued for the remainder of the Treatment Period; unless the subject meets the criteria for insulin lispro re-introduction (see Section [5.1.3.5](#)).

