8.3.3.2. Other Comparisons of Interest

A key secondary endpoint is the proportion of subjects treated with once-weekly albiglutide that are able to replace prandial insulin without the need for re-introduction of insulin lispro. The 95% confidence interval of the sample proportion will be estimated, stratified by region, age category, and current use of metformin.

The proportion of subjects with hypoglycemia, as confirmed by plasma glucose monitoring <70 mg/dL (<3.9 mmol/L) and/or requiring third-party intervention through Week 26, will be compared between treatment groups, adjusting for baseline HbA_{1c} stratum, age group, current use of metformin, and region.

Other binary secondary endpoints, such as the proportion of subjects achieving HbA_{1c} treatment goals at Week 26 and the proportion of subjects achieving composite secondary endpoints (i.e., criteria involving HbA_{1c} target and hypoglycemia) will be analyzed analogous to the proportion of subjects with hypoglycemia.

Continuous secondary endpoints, e.g., changes over time in HbA_{1c}, FPG, and body weight, changes in daily insulin dose, changes in mean daily blood glucose based on 8-point SMBG, and changes in total number of weekly insulin injections will be summarized descriptively and analyzed using an MMRM (observed data). In the MMRM for non-HbA_{1c} endpoints, the corresponding baseline variable will be modeled as a covariate (in place of baseline HbA_{1c}) for variance reduction and to adjust for any baseline differences in treatment groups attributable to chance as well as the randomization stratification variables (HbA_{1c} stratum, age category, current use of metformin).

The number of hypoglycemic events with confirmed home blood glucose monitoring <70 mg/dL (<3.9 mmol/L) and/or requiring third-party intervention in 3-month intervals (i.e., from Baseline/Randomization to Week 12, >Week 12 to Week 26) will be compared between the treatment groups using a Poisson regression model with offset for the person-year, which will include treatment effect and covariates such as HbA_{1c} stratum, age (<65 years versus ≥65 years), current use of metformin (metformin use versus no metformin use), and region.

The time to meeting prespecified criteria for severe, persistent hyperglycemia at Week 26 will be analyzed for treatment group differences using pairwise log-rank tests within a Kaplan-Meier model.

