8.3.5.1. Hypoglycemic Events

Hypoglycemic events merit special attention in the development and study of drugs for the treatment of T2DM since they are often related to the efficacy of a compound. In order to accomplish this, hypoglycemic event data including supplemental hypoglycemic event information not collected on AE eCRF page are reported on a separate hypoglycemic event eCRF page. However, any hypoglycemic event that meets the criteria for a serious AE will also be included in the serious AE summaries.

Analysis of on-therapy hypoglycemic events will include all AEs coded to the preferred term of 'Hypoglycemia'. For on-therapy hypoglycemic events the number and percentage of subjects with events, the number of events, the incidence rate (per 100 person-years) and AE density (per 100 person-years) by the severity of the event defined by American Diabetes Association [ADA], SAE status, relationship to the investigational product, and withdrawal status will be summarized by treatment group. The events will also be summarized according to intervention provided, action taken with regard to background and anti-hyperglycemic medications and onset week and glucose levels. All hypoglycemic events will be classified as severe, documented symptomatic,

asymptomatic, probable symptomatic, or pseudohypoglycemia per the American Diabetes Association criteria) criteria.

The number of events of hypoglycemia with confirmed home blood glucose monitoring < 3.9 mmol/L and/or requiring third party intervention (i.e., severe, documented symptomatic and asymptomatic hypoglycemic events) in 3 monthly intervals (i.e., from Baseline to Week 12, >Week 12 to Week 26) will be summarized by treatment group. The exposure-adjusted event rate will be compared between treatment groups using a Poisson regression model with offset for the person-year, which will include HbA_{1c} stratum, age (<65 years versus ≥65 years), current use of metformin (metformin use versus no metformin use), and region as covariates.

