5. Example SAS code for analysis on FPG change from baseline by baseline FPG tertiles

```
ODS OUTPUT LSMeans= OUTLIBNAME.LSMeans SLICES= OUTLIBNAME.Diffs;
PROC MIXED DATA= INDATA;
  CLASS USUBJID TRT01PN REGION METFORMIN AGEGR1 HBGR1 FPG_TTL
    AVISITN;
  MODEL CHG= FPG_TTL HBGR1 TRT01PN REGION METFORMIN AGEGR1
    AVISITN TRT01PN*AVISITN TRT01PN*FPG_TTL
    FPG_TTL*AVISITN TRT01PN*FPG_TTL*AVISITN /DDFM =KR;
  REPEATED AVISITN/SUB=USUBJID TYPE=UN;
  LSMEANS TRT01PN*FPG_TTL*AVISITN/SLICE=AVISITN CL DIFF;
  ESTIMATE 'Treatment difference at Week 26 for 1st Baseline FPG
  Tertile'
    TRT01PN -1 1
    TRT01PN*AVISITN      0 0 0 0 1 0 0 0 0 -1
```

```
TRT01PN*FPG_TTL*AVISITN 0 0 0 0 1 0 0 0 0 0  
0 0 0 0 0 0 0 0 0 0 -1  
0 0 0 0 0 0 0 0 0 0 /CL ;  
RUN;
```

5. Example SAS code for analysis on exposure-adjusted event rate with Poisson regression model

```
ODS OUTPUT LSMeans= Lsmeans Diffs=Diffs;  
proc genmod data=INDATA;  
  class USUBJID TRT01AN MCRIT2ML HBGR1 AGEGR1 METFMN CTRYGR1;  
  model NUMEVT1=TRT01AN MCRIT2ML HBGR1 AGEGR1 METFMN CTRYGR1/  
d=poisson offset=PYOFFSET;  
  repeated SUBJECT=USUBJID /corrw covb type=exch;  
  LSMEANS TRT01AN/ EXP ILINK E CL DIFF;  
run;
```

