No.	Population	IDSL / TST ID / Example Shell	Title	Programming Notes	Deliverable [Priority]
3.61	Safety		Overview of On-therapy Adverse Events of Special Interest		
3.71	Safety		On-therapy Hypoglycemic Events by SAE Status, Relationship to Study Medication, and Withdrawal Status		
3.72	Safety		On-therapy Hypoglycemic Events by Treatment, Symptom, Severity, Intervention and Action Taken		
3.73	Safety		On-therapy Hypoglycemic Events by Blood Glucose Level		
3.74	Safety		On-therapy Daytime and Nocturnal Hypoglycemic Events		
3.75	Safety		On-therapy Hypoglycemic Events with Confirmed Home Plasma Glucose Monitoring <3.9 mmol/L and/or Requiring Third Party Intervention by Intervals for Time of Onset		
3.76	Safety		Analysis of Exposure-adjusted Incidence Rate of On-therapy Severe, Documented Symptomatic or Asymptomatic Hypoglycemic Events		
3.77	Safety		Analysis of Exposure-adjusted Incidence Rate of On-therapy Severe Hypoglycemic Events		
3.78	Safety		Analysis of Exposure-adjusted Incidence Rate of On-therapy Documented Symptomatic Hypoglycemic Events		
3.79	Safety		Analysis of Exposure-adjusted Incidence Rate of On-therapy Asymptomatic Hypoglycemic Events		
3.80	Safety		On-therapy Hypoglycemic Events Over Time by Onset Week		
3.91	Safety		On-therapy and Post-therapy Cardiovascular Adverse Events		
3.101	Safety		On-therapy and Post-therapy Thyroid Adverse Events Reported by the Investigator		

Safety : Tables					
No.	Population	IDSL / TST ID / Example Shell	Title	Programming Notes	Deliverable [Priority]
3.102	Safety		On-therapy and Post-therapy Thyroid Adverse Events Identified by a Customized MedDRA Query		
3.111	Safety		Summary of Gastrointestinal Adverse Events		
3.112	Safety		On-therapy Gastrointestinal Adverse Events		
3.113	Safety		On-therapy Serious Gastrointestinal Adverse Events		
3.114	Safety		On-therapy Treatment-related Gastrointestinal Adverse Events		
3.115	Safety		On-therapy Gastrointestinal Adverse Events Leading to Permanent Discontinuation of Study Treatment before Scheduled End of Treatment Period		
3.116	Safety		On-therapy Gastrointestinal Adverse Events Over Time		
3.117	Safety		On-therapy Gastrointestinal Adverse Events by Onset Week		
3.118	Safety		Kaplan-Meier Analysis of Time to First Occurrence of On-therapy Gastrointestinal Adverse Event		
3.119	Safety		On-therapy Nausea Over Time		
3.120	Safety		On-therapy Diarrhea Over Time		
3.121	Safety		On-therapy Vomiting Over Time		
3.122	Safety		On-therapy Nausea or Vomiting Over Time		

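### The SAP reduces the protocol's by-interval Poisson comparison of hypoglycemic events to a single rate ratio and does not record the change

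*SAP*

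**What the plan says.** **Protocol 8.3.3.2.** Confirmed or assisted hypoglycemic events "in 3-month intervals (i.e., from Baseline/Randomization to Week 12, >Week 12 to Week 26) will be compared between the treatment groups" by Poisson regression with a person-year offset. The covariates named are HbA1c stratum, age group, metformin use and region. No interval term or interaction is named. The same two intervals appear in the hypoglycemia endpoint in Protocol section 2 and SAP 2.2.

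**SAP 8.3.5.1.** The protocol's sentence is split in two. The counts for "Baseline to Week 12, >Week 12 to Week 26) will be summarized by treatment group". Then: "The exposure-adjusted event rate will be compared between treatment groups using a Poisson regression model with offset for the person-year". No interval is attached to the second statement.

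**SAP 11.11.1 (example code for the exposure-adjusted event rate).** The model line is "model NUMEVT1=TRT01AN MCRIT2ML HBGR1 AGEGR1 METFMN CTRYGR1". A REPEATED statement uses subject with exchangeable correlation, and LSMEANS is requested for `TRT01AN` alone. There is no BY statement and no product term. `MCRIT2ML` is not defined in either document.

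**SAP 11.14.6.** Table 3.75 shows events by interval of onset, and its title names no analysis. Tables 3.76 to 3.79 carry the modelled analyses, and no interval appears in their titles.

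**SAP 2.1.** The list of changes from the protocol has one entry, on insulin dose. The hypoglycemia comparison is not in it.

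**The concern.** A team that follows the SAP will not produce a comparison that the protocol specifies, and nothing records that it was dropped.

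The intervals matter because the insulin contrast is not constant by design. In the albiglutide arm lispro is halved at baseline, stopped at Week 4, and may return after Week 8. In the control arm titration starts with the basal insulin: "After about 6 weeks, it is expected that the basal insulin glargine dose will have been stabilized and the insulin lispro titration may begin". A rate ratio that differs before and after Week 12 is therefore plausible, though not certain.

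If `MCRIT2ML` is the interval, the coded model forces the same ratio on both intervals. If it is something else, interval is not in the model at all. In either case a reader of the modelled tables would get one average, with no adjusted estimate or confidence interval for the early or the late period.

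**Working it through.** **No figure to reproduce.** The documents state no event rate, rate ratio or power for this model. The only related figure is the background statement of 1.5- to 2-fold less symptomatic hypoglycemia, that is, ratios of 1/1.5 = 0.67 to 1/2 = 0.50. That range comes from two earlier studies, not from two intervals.

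**What the coded model estimates.** Take equal arms, intervals of t = 12 and 14 weeks, control rates r1 and r2, and true ratios RR1 and RR2. With interval as a main effect only, the Poisson score equation gives

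common ratio = (12·r1·RR1 + 14·r2·RR2) / (12·r1 + 14·r2).

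With equal control rates (an assumption):

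| True ratios | Common ratio |
|---|---|
| 1.0 / 0.5 | (12 + 7)/26 = 0.73 |
| 0.9 / 0.5 | (10.8 + 7)/26 = 0.69 (0.685) |
| 0.8 / 0.5 | (9.6 + 7)/26 = 0.64 |
| 0.67 / 0.5 | (8.04 + 7)/26 = 0.58 |
| 0.6 / 0.6 | 0.60 |

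Letting the control rate differ 1.5-fold between intervals moves the 1.0/0.5 case from (12 + 10.5)/33 = 0.68 to (18 + 7)/32 = 0.78.

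**Simulation of the model as coded.** Assumptions: 397 per arm, control rate 8 per person-year, gamma frailty variance 1, exchangeable GEE, 60 simulated trials per scenario, no dropout.

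| True ratios | Single ratio | Its 95% CI covers the first / second true ratio | Ratios with the interaction added |
|---|---|---|---|
| 1.0 / 0.5 | 0.75 | 7% / 0% | 1.00 / 0.50 |
| 0.9 / 0.5 | 0.71 | 18% / 2% | 0.92 / 0.51 |
| 0.8 / 0.5 | 0.65 | 18% / 10% | 0.81 / 0.50 |
| 0.6 / 0.6 | 0.61 | 92% / 92% | 0.61 / 0.61 |

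With 60 trials these coverages are approximate.

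**Cost in precision.** In a second assumed scenario (control 8 then 10 events per person-year, albiglutide 7 then 3, frailty variance 1.2) the single ratio was 0.53; by the formula, (12·7 + 14·3)/(12·8 + 14·10) = 126/236 = 0.53. The standard error of its log was 0.087. With the interaction, the interval ratios were 0.87 and 0.30, with standard errors 0.093 and 0.100. Relative increase: 0.093/0.087 = 1.07 and 0.100/0.087 = 1.15.

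**A milder case.** At 0.67/0.50 the common ratio is 0.58. Carrying over the standard error of 0.087, its 95% CI is 0.578 × exp(±1.96 × 0.087) = 0.49 to 0.69, which contains both interval ratios.

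**The case against.** Several points on the other side stand.

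- The protocol's covariate list names no interval or interaction term, so the commitment rests on its statement that the interval counts will be compared. SAP 8.3.5 also defines the event rate for a given period, so 8.3.5.1 could be read as period-specific. The code is labelled an example, and table shells are kept in a separate document. This softens the departure but does not remove it: neither the code nor any table title provides an interval contrast.
- A reader might infer that the single ratio can fit neither interval. That does not follow. It fits both if the ratio is constant, and at 0.67/0.50 its interval could cover both.
- A reader might infer that the trial could not say whether any hypoglycemia advantage is early, late or throughout. That is too strong. Table 3.75 gives events by interval, and Table 3.80 and Figure 3.01 give them by onset week and arm. What is missing is the adjusted, interval-specific ratio with its confidence interval.
- The Week 4 stop, the start of control lispro titration at about Week 6, and the possible re-introduction after Week 8 all begin inside the first interval. A first-interval ratio would still average over those phases.
- More than one record per subject is inferred from the REPEATED statement; the input data set is not described.
- The key secondary hypoglycemia endpoint is the percentage of subjects with an event, tested by CMH. The Poisson analysis is not in the hierarchy of SAP Appendix 10.

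Tables 3.76 to 3.79 are titled as incidence rates although the model counts events. A reader might take this as a further modelling error. Protocol 8.3.5.2 itself defines the exposure-adjusted incidence rate by events, while SAP 8.3.5 reserves the term for subjects, so this is a terminology mismatch and a side note only.

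**Conclusion.** The point holds in a limited form. The protocol specifies a between-arm comparison of event counts in two intervals; the SAP as written yields one treatment rate ratio, leaves `MCRIT2ML` undefined, and does not list the change in 2.1. That much rests on the documents alone.

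The consequence is conditional on the ratio differing between intervals. The single figure is then a weighted average that may misstate one or both intervals, by an amount that depends on rates, ratios and dispersion that the documents do not give. No confirmatory conclusion changes. The correction is worth making because it restores a specified analysis at little cost.

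**What to change.** In SAP 11.11.1, define `MCRIT2ML`, or replace it with a named interval variable. Add the treatment-by-interval product to the MODEL statement and request least squares means for that product. In SAP 8.3.5.1 and Tables 3.76 to 3.79, report the rate ratio with 95% CI for Baseline to Week 12 and for after Week 12 to Week 26, plus the interaction p-value, and keep the overall ratio as a further row. If a single ratio is preferred, enter that choice and its reason in SAP 2.1. Use one term for the event-based rate in the text and the table titles.

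The cost is one model term, a few table rows and SAP wording; no new data are needed. The interval-specific confidence intervals will be somewhat wider than the overall one, which is retained.

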11.12. Appendix 12: Sample Size Considerations

The primary hypothesis to be tested is that albiglutide plus insulin glargine (with or without metformin) will provide glycemic control (as measured by HbA_{1c} change from Baseline) noninferior to insulin lispro plus insulin glargine (with or without metformin) after 26 weeks of treatment in subjects with T2DM inadequately controlled on their current regimen of basal-bolus insulin therapy. If the null hypothesis of albiglutide inferiority is rejected, a test of superiority will be applied.

Approximately 794 subjects will be randomly assigned in a 1:1 ratio to 2 treatment groups. Eligible subjects will be stratified by screening HbA_{1c} value (<8.0% versus ≥8.0%), age (<65 years versus ≥65 years), and use of metformin (metformin use versus no metformin use). Assuming that 15% of subjects will be withdrawn early or will be lost to follow-up, approximately 337 subjects in each treatment group will complete 26 weeks of study assessments.

With 337 completed subjects in each of the 2 treatment groups, the study will have at least 90% power to reject the null hypothesis of inferiority for HbA_{1c} change from Baseline, assuming a non-inferiority margin of 0.3%, an expected treatment group difference of 0.0%, and a standard deviation of 1.2%, using a 2-sample, 1-sided t test with a test-wise significance level of 0.025.

If non-inferiority of albiglutide is established, superiority of albiglutide versus insulin lispro will be tested. Given the sample size of 337 completed subjects per treatment group and assuming a common standard deviation of 1.2, the minimum detectable difference in means between albiglutide and insulin lispro resulting in a significant test is 0.18, with a power of 50% and a type I error rate of 0.05.

11.13. Appendix 13: Abbreviations & Trade Marks

11.13.1. Abbreviations & Trade Marks

List of Abbreviations

AE	Adverse Event
AIC	Akaike information criterion
ALP	alkaline phosphatase
ALT	alanine aminotransferase
AST	aspartate aminotransferase
β -HCG	β -human chorionic gonadotropin
CMH test	Cochran-Mantel-Haenszel test
CV	cardiovascular
dL	deciliter
ECG	electrocardiogram
eCRF	electronic case report form
eGFR	estimated glomerular filtration rate
FA	full analysis
FPG	fasting plasma glucose
FSG	fasting serum glucose
g	gram
GCP	Good clinical practice
GI	gastrointestinal
GSK	GlaxoSmithKline
HbA _{1c}	glycosylated hemoglobin
HFS-II	hypoglycemia fear survey-II
ICH	International Conference on Harmonisation
IU	international unit
kg	kilogram
L	liter
LMCF	last mean carried forward
m	meter
MAR	missing at random
MedDRA	Medical Dictionary for Regulatory Activities
mg	milligram
MI	myocardial infarction
min	minute
mL	milliliter
mmol	millimole
MMRM	mixed-effect model with repeated measures
MNAR	missing not at random
PK	pharmacokinetic
PP	per-protocol
PT	Preferred Term
RAP	reporting and analysis plan
SAC	Statistical Analysis Complete
SAE	serious adverse event

SMBG	self-monitored blood glucose
SOC	System Organ Class
SU	sulfonylurea
T2DM	type 2 diabetes mellitus
TEAE	Treatment Emergent Adverse Event
TRIM-Diabetes	treatment-related impact measure for diabetes
TSH	thyroid-stimulating hormone
ULN	upper limit of normal

Trademark Information

Trademarks of the GlaxoSmithKline group of companies
None
Trademarks not owned by the GlaxoSmithKline group of companies
HFS-II
Humalog
Lantus
MedDRA
TRIM-Diabetes

11.14. Appendix 14: List of Data Displays

11.14.1. Data Display Numbering

The following numbering will be applied for RAP generated displays:

Section	Tables	Figures
Study Population	1.01 to 1.46	N/A
Efficacy	2.01 to 2.701	2.01 to 2.92
Safety	3.01 to 3.348	3.01 to 3.71
Other Analysis		
Section	Listings	
ICH Listings		1 to 44
Other Listings		101 to 170

11.14.2. Mock Example Numbering

Non IDSL specifications will be referred as detailed below and where appropriate an example mock-up table is provided in a separate shell document:

Section	Figure	Table	Listing
Study Population			
Efficacy			
Safety			
Other Analysis			

NOTE:

- Non-Standard displays are indicated in the IDSL / TST ID / Example Shell' or Programming Notes' column as '[Non-Standard] + Reference.'

11.14.3. Study Population Tables

Study Population Tables					
No.	Population	IDSL / TST ID / Example Shell	Title	Programming Notes	Deliverable [Priority]
Subjection Disposition, Demographics and Baseline Characteristics					
1.01	FA		Subject Disposition		
1.02			Summary of Study Enrollment and Reasons for Screening Failures and Standardization Failures		
1.03	FA		Reasons for Withdrawal from Study		
1.04	FA		Reasons for Discontinuing Study Treatment		
1.05	FA		Subject Status by Visit		
1.06	FA		Subjects Randomized across Sites		
1.07	FA		Inclusion/Exclusion Criteria Deviations		
1.08	FA		Significant Protocol Deviations		
1.09	FA		Demographics and Baseline Characteristics		
1.10	FA		Geographic Ancestry		
1.11	FA		Substance Use		
Medical History					
1.21	Safety		Medical and Family History Status		
1.22	Safety		Current and/or Past Cardiovascular Medical History		
1.23	Safety		Current and/or Past Diabetes Related Conditions		
1.24	Safety		Duration of Diabetes Disease History		
1.25	Safety		Current and/or Past Medical/Surgical Procedure History		
1.26	Safety		Current and/or Past Gastrointestinal Medical Conditions		
1.27	Safety		Current and/or Past Nephropathy (Including Microalbuminuria) and Kidney Injury History		

Study Population Tables					
No.	Population	IDSL / TST ID / Example Shell	Title	Programming Notes	Deliverable [Priority]
1.28	Safety		Current and/or Past Cancer History		
1.29	Safety		Current and/or Past Pneumonia Medical History		
1.30	Safety		Current and/or Past Skin Medical Conditions		
1.31	Safety		Current and/or Past Thyroid Medical History		
1.32	Safety		Current and/or Past Other Medical History		
Medications and Non-drug Therapies					
1.41	Safety		Prior Medications		
1.42	Safety		Concomitant Medications		
1.43	Safety		Post-therapy Medications		

